7.0 REQUIRED OBSERVATIONS/MATERIAL AND DATA TO BE ACCESSIONED

7.1 Clinical and Laboratory Studies

All entry/eligibility studies must be performed within one week prior to study enrollment (“PreEnrollment”) unless specified otherwise (e.g., Disease evaluation is required within two weeks prior to study enrollment. Obtain other studies as needed for good patient care.) Some evaluations will need to be performed within 3 days prior to starting therapy (“Pre-Treatment”).

STUDIES TO BE OBTAINED	Pre-Enrollment*	Pre-Treatment (within 3 days prior to starting protocol therapy)	During Course 1 (Cohort A and B)	During Course 1 (Cohort C)	Final Visit/ Follow-up
History	X	X			X
Physical Exam	X	X	Weekly	Weekly	X
Vital Signs	X	X	Weekly	Weekly	X
Height, Weight, BSA	X	X			X

STUDIES TO BE OBTAINED	Pre-Enrollment*	Pre-Treatment (within 3 days prior to starting protocol therapy)	During Course 1 (Cohort A and B)	During Course 1 (Cohort C)	Final Visit/ Follow-up
CBC, differential, platelets	X	X	Twice weekly including at least within 1 day prior to Marqibo® doses #2, 3 and 4	Twice weekly	X
Chemistries ¹	X	X	Twice Weekly, including at least within 1 day prior to Marqibo® doses #2, 3 and 4	Twice weekly	X
Electrolytes ²	X	X	Twice Weekly, including at least within 1 day prior to Marqibo® doses #2, 3 and 4	Twice weekly	X
HIV	X [^]				
HBsAg, HCV	X [^]				
Urine pregnancy or Serum β-HCG (for females of childbearing potential)	X		If pregnancy is suspected	If pregnancy is suspected	
Echocardiogram/ MUGA/Cardiac MRI	X [^]				

STUDIES TO BE OBTAINED	Pre-Enrollment*	Pre-Treatment (within 3 days prior to starting protocol therapy)	During Course 1 (Cohort A and B)	During Course 1 (Cohort C)	Final Visit/ Follow-up
Neurological Examination/ Completion of Neurological Exam Form (Appendix 4).	X	X	Weekly including at least within 1 day prior to Marqibo® doses #2, 3 and 4	Weekly	X
EKG	X		Day 8 (+/- 2 days) [cohort A only]		
CSF Cell count and Differential (with IT Therapy if needed as per Section 4.1)	X [^]		At the time of LP for IT therapy and at restaging on day 29 [†] (+/- 2 days)	At the time of LP for IT therapy if given and at restaging on day 14 (+2) or day 29 (+/-2) if 2 cycles are given [§]	
Bone marrow aspirate and/or biopsy for response assessment (Section 7.3)	X [^]		Day 29 (+/- 2 days)	Day 14 (+2) or day 29 (+/-2 days) [§]	
Bone marrow sample for MRD	X ^{^#} Bone marrow need not be repeated for this purpose.		Day 29 (+/- 2 days)		
Pharmacokinetic Studies (required) May be collected through the line used for Marqibo® infusion.			Immediately prior to Marqibo administration for Marqibo doses #1, 2, and 3 for arm A and B.	Arm C will be obtained prior to Dose 1 and a trough level on day 8, during each cycle.	

STUDIES TO BE OBTAINED	Pre-Enrollment*	Pre-Treatment (within 3 days prior to starting protocol therapy)	During Course 1 (Cohort A and B)	During Course 1 (Cohort C)	Final Visit/ Follow-up
Peripheral Blood for Pharmacokinetic Studies (optional)			Day 1 (3 blood samples)	Day 1 (3 blood samples)	
Follow-up visit					Q 6months

*Required for verification of eligibility. FAX or email all results to the TACL Operations Center with study registration eligibility. If a patient has labs done prior to study entry that establish eligibility, then abnormal Day 1 labs do not deem them ineligible.

#Optional

^Within 2 weeks prior to enrollment is acceptable

†IT chemotherapy is not required at the time of day 29 LP, but can be given per investigator discretion.

§Cohort C disease restaging will be done after cycle 1, if only one cycle is administered. If a second cycle is planned, restaging may be done after cycle 2. Please see section 7.3 for additional guidance. A lumbar puncture will only be required after 2 cycles; and is optional after cycle 1.

1: BUN, creatinine, ALT, AST, LDH, alkaline phosphatase, glucose, total and direct bilirubin, albumin, total protein, uric acid

2: Sodium, potassium, chloride, bicarbonate, calcium, magnesium, phosphorus

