4.1 Treatment Course

Only 1 course of treatment will be permitted. Upon completion of treatment on this study, plans for additional therapy will be at the discretion of the treating team.

As of Amendment 3, cohorts A and B will be treating at dose level 1; Cohort C will be treating at dose level 2.

Marqibo Dose Levels

Dose Level 1: 1.5 mg/m²

Dose Level 2: 2.0 mg/m²

Cohort A:

	Day 1	Day 2	Day 3	Day 4	Day 5	Day 8	Day 15	Day 16	Day 17	Day 18	Day 19	Day 22	Day 29
Marqibo®	●					●	●					●	Response Evaluator
Dexamethasone	●	●	●	●	●		●	●	●	●	●		
Mitoxantrone	●	●											
Pegaspargase#			●						●				
IT Methotrexate	●					●							

asparaginase Erwinia chrysanthemi (Erwinaze®), crisantapase (Erwinase®) asparaginase Erwinia chrysanthemi (recombinant)-rywn (Rylaze®) may be substituted for allergy to Pegaspargase. See below.

Drug Administration Order

Marqibo will be administered first. Mitoxantrone will follow Marqibo administration on day 1 with dexrazoxane to be given immediately before mitoxantrone (when dexrazoxane is utilized [optional]). Timing of IT methotrexate is flexible in regards to the timing of Marqibo, but should not be given simultaneously in order to reduce the risk of administration route error.

Marqibo® (Dose level 1 only as of Amendment 3)

- Dose Level 1: 1.5 mg/m²/dose (no dose cap) given IV over 60 minutes (±10 minutes) on days 1, 8, 15 and 22.
- ~~Dose Level 2: 2 mg/m²/dose (no dose cap) given IV over 60 minutes (±10 minutes) on days 1, 8, 15 and 22.~~
- Review list of concomitant medications that are prohibited (CYP3A4 inhibitors) or to be used with caution (Appendix 3). See section 4.5 for drug interactions.
- Dose will be given over 60 minutes ± 10 minutes

Dexamethasone

- 20 mg/m²/day divided BID given orally on days 1 through 5 and 15 through 19. The two doses should be separated by at least 8 hours
- Any oral formulation of dexamethasone is acceptable
- IV may be given if oral formulation is not tolerated (please document reason or al could not be given)

Mitoxantrone

- 10 mg/m²/day given on days 1 and 2 as a short IV infusion over 5-15 minutes. Do not infuse over less than 3 minutes.
- Dose will be given over 5-15 minutes
- See section 5.6 for guidance on optional cardioprotection.

Pegaspargase

- 2,500 international units/m²/day IM or IV on days 3 and 17. **(Cap individual dose at 3,750 IU, based on vial size)**

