4.3.1 Marqibo®

4.3.1.1 Weekly assessment of neurologic function should be performed prior to administration of Marqibo®. (Appendix 4).

- Subjects who develop grade 3 or greater sensory or motor neuropathy will discontinue Marqibo® treatment.
- Subjects with < grade 3 neuropathy will be closely monitored without any adjustment to Marqibo® dose

4.3.1.2 Dosing will NOT be held for cytopenias.

4.3.1.3 Transaminase elevation: Marqibo® dosing will be delayed for grade 3 or higher AST (aspartate aminotransferase) or ALT (alanine aminotransferase) elevation

until resolution to grade 2 or baseline, then resume full dose. Maximum allowable delays are specified in section 4.3.

4.3.1.4 Hyperbilirubinemia:

Bilirubin Level	Dose Delay
Total bilirubin < 1.5 x upper limit of normal and direct bilirubin < 1.4 mg/dL	None, administer full dose
Total bilirubin > 1.5 x upper limit of normal, and/or direct bilirubin \geq 1.4 mg/dL	Withhold dose until resolution to grade 1 bilirubin or baseline and direct bilirubin < 1.4, then resume full dose. Maximum allowable delays are specified in section 4.3.

For subjects with documented Gilbert's disease, no modification is necessary unless the total bilirubin exceeds 5 x ULN or the direct bilirubin is \geq 1.4 mg/dL.

4.3.1.5 Jaw Pain: Treat with analgesics; do not modify Marqibo® dose.

4.3.1.6 Extravasation: In the event of an extravasation, discontinue the IV administration of the drug and institute appropriate measures according to institutional guidelines.

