4.3.1.7 Drug Interactions: See Section 4.4

4.3.2 Pegaspargase

4.3.2.1 Allergic Reactions

Local Reactions (inflammation at injection site, swelling): Continue pegaspargase administration in the presence of Grade 1 allergy (transient flushing or rash; drug fever < 38°C).

Anaphylaxis/Systemic Allergic reactions: Systemic allergy is associated with the presence of pegaspargase neutralizing antibodies, which render asparaginase therapy ineffective. Discontinue if the patient develops a systemic allergic reaction (urticaria, wheezing, laryngospasm, hypotension, etc).

4.3.2.2 Coagulopathy: If symptomatic, hold pegaspargase until symptoms resolve, allowing for up to a one-week delay in scheduled dosing or resume with the next scheduled dose. Consider factor replacement (FFP, cryoprecipitate, factor

VIIa). Do not withhold dose for abnormal laboratory findings without clinical symptoms.

4.3.2.3 Hyperbilirubinemia: Pegaspargase should be held in patients with an elevated direct bilirubin ≥ 1.4 mg/dL. Resume when direct bilirubin < 1.4 mg/dL, may give within one week of scheduled dosing.

Direct Bili	Dose modification
≤ 3 mg/dL	Full dose
3.1-5 mg/dL	Hold asparaginase and result when direct bilirubin ≤ 2 mg/dL
>5 mg/dL	HOLD asparaginase; do not substitute other asparaginase products; do not make up missed doses

4.3.2.4 Hyperglycemia: Do not modify dose. Treat hyperglycemia as medically indicated.

4.3.2.5 Hyperlipidemia: Do not modify dose.

4.3.2.6 Ketoacidosis: Hold pegaspargase until blood glucose can be regulated with insulin.

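### Section 4.3.2.3 gives two incompatible direct-bilirubin rules for pegaspargase in Cohorts A and B: between 1.4 and 3.0 mg/dL the text says hold and the table says full dose

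*Combined protocol and SAP*

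**What the plan says.** Section 4.1 gives pegaspargase in Cohort A at "2,500 international units/m²/day IM or IV on days 3 and 17", and Cohort B follows the same instructions without mitoxantrone. Cohort C receives none.

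Section 4.3.2.3 sets the bilirubin rule twice:

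- **Text.** Hold at a direct bilirubin of 1.4 mg/dL or more. Then: "Resume when direct bilirubin < 1.4 mg/dL, may give within one week of scheduled dosing".
- **Table directly below.** Full dose at 3 mg/dL or less. At 3.1 to 5 mg/dL: "Hold asparaginase and result when direct bilirubin ≤ 2 mg/dL" (the verb is evidently meant to be *resume*). Above 5 mg/dL, hold, and "do not substitute other asparaginase products; do not make up missed doses".

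For Marqibo, section 4.3.1.4 acts when direct bilirubin is 1.4 mg/dL or more, or when total bilirubin exceeds 1.5 times the upper limit of normal: "Withhold dose until resolution to grade 1 bilirubin or baseline and direct bilirubin < 1.4, then resume full dose". The direct-bilirubin limit of 1.4 mg/dL also applies to patients with Gilbert's disease.

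Section 7.1 ties on-treatment laboratory draws to Marqibo only: "Twice weekly including at least within 1 day prior to Marqibo® doses #2, 3 and 4". That is the blood-count row; the chemistries row, which covers direct bilirubin, sets the same timing.

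**The concern.** A dose-modification rule has to give one instruction for one laboratory value. Here a treating physician with a direct bilirubin of, say, 2.0 mg/dL on a pegaspargase day can cite the protocol for holding the dose or for giving it in full. Two sites could treat identical patients differently, and neither would be in breach.

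What is at stake is patient safety. Section 6.5.2 lists abnormal liver function tests as an occasional effect of pegaspargase. Section 6.5.1 gives a half-life of 5.73 days, so a dose cannot be taken back once given. Section 2.2 warns that hepatotoxicity risk may rise when Marqibo is combined with other hepatotoxic agents. Under the table, pegaspargase could go ahead at full dose in a patient whose Marqibo would be withheld on the same result.

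**Working it through.** The plan states no figure to reproduce here. The check is to apply each rule to the same direct bilirubin value.

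Inputs: the hold, resume and late-dose limits in the 4.3.2.3 text; the three rows of the 4.3.2.3 table; the direct-bilirubin limit in 4.3.1.4; the dosing days in 4.1.

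**Step 1: dose or hold.**

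| Direct bilirubin (mg/dL) | 4.3.2.3 text | 4.3.2.3 table | Marqibo, 4.3.1.4 | Text and table agree? |
|---|---|---|---|---|
| 1.3 | full dose | full dose | full dose, if total bilirubin also allows | yes |
| 1.4 | hold | full dose | withhold | no |
| 2.0 | hold | full dose | withhold | no |
| 3.0 | hold | full dose | withhold | no |
| 3.1 | hold | hold | withhold | yes on the hold |
| 5.0 | hold | hold | withhold | yes on the hold |
| 5.1 | hold | hold | withhold | yes on the hold |

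The instructions are opposite from 1.4 to 3.0 mg/dL, a band 3.0 − 1.4 = 1.6 mg/dL wide. Throughout that band Marqibo is withheld.

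**Step 2: when to resume.** The text resumes below 1.4 mg/dL, the table at 2 mg/dL or less. Take a patient held under both rules at 4 mg/dL who falls to 1.8 mg/dL. The table releases the dose and the text does not. For a patient already on hold in the 3.1 to 5 row, the rules differ from 1.4 to 2.0 mg/dL.

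**Step 3: late doses.** The text allows a held dose within one week of schedule: up to day 3 + 7 = 10 for the first dose and day 17 + 7 = 24 for the second. It makes no exception for high values. The table bars a make-up dose once the value has exceeded 5 mg/dL. A patient at 5.1 mg/dL on day 3 who is below 1.4 mg/dL by day 8 gets the dose under the text and loses it under the table.

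**Step 4: primary endpoint.** Section 9.1.1 requires 1 of 2 pegaspargase doses, so 2 − 1 = 1 dose can be lost without failing that dose criterion. Both doses would have to be missed before the choice of rule could matter through it.

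**The case against.** Four arguments deserve an answer.

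*One of the two rules may be superseded text whose strike-through was lost.* The file does carry redlined text, and 4.3.2.7 nearby contains a stray fragment that suggests incomplete editing. But deleted text is shown with strike marks elsewhere (the Cohort A dose level 2 line and the Cohort C transaminase rule, both in 4.1), and 4.3.2.3 shows none. The possibility cannot be excluded, but it is weak. If one rule is a leftover, it still needs removing.

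*The table may be meant for Erwinia asparaginase.* It has no such label, sits under pegaspargase, and forbids substituting other asparaginase products.

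*The threshold is a clinical choice, and the text rule withholds an active drug.* This stands. The investigators should confirm the limit.

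*Few patients may be affected.* This also stands. Section 6.5.2 lists hyperbilirubinemia itself as rare, and 3.3.5 requires total bilirubin of at most 1.5 times the upper limit at entry, with an exception for Gilbert's disease. The documents do not say how often direct bilirubin falls between 1.4 and 3.0 mg/dL.

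A reader might also infer that the value behind the hold can be badly out of date, because no draw is timed to pegaspargase. The documents do not make that a defect. An age of 5 days on day 3 needs a pre-treatment draw at the edge of its 3-day window (3 + 2 = 5) and both first-week draws after day 3. It falls to 3 days if twice weekly means no gap above 4 days. The 3 days on day 17 (17 − 14) assumes that Marqibo dose 3 is on schedule; if Marqibo has stopped, 8 days is possible. A footnote to 7.1 mentions Day 1 laboratory results, and 7.1 allows further tests as care requires. This is a scheduling preference.

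**Conclusion.** The contradiction is real and needs no assumption beyond reading 4.3.2.3 as printed. It has three parts: opposite dosing orders from 1.4 to 3.0 mg/dL, different resume limits (below 1.4 versus 2 mg/dL or less), and a one-week late dose that the table rules out above 5 mg/dL. It is a patient-safety clarification that merits a correction, not a threat to the trial's conclusions.

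Two stronger inferences are not supported. First, section 9.2 reports a hepatic DLT and a near-DLT before the Cohort B de-escalation, but it frames them as known hepatic toxicity of Marqibo. Nothing in the available text links any event to the pegaspargase rule. Sections 2.4.1 and 2.4.2, which 4.0 cites for experience to date, were not available for this review. Second, no effect on the primary endpoint is shown.

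**What to change.** Amend 4.3.2.3 so that text and table state one rule. The proposed default is the text rule, because it matches the Marqibo direct-bilirubin limit in 4.3.1.4:

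| Direct bilirubin | Pegaspargase |
|---|---|
| < 1.4 mg/dL | Full dose |
| 1.4–5 mg/dL | Hold; resume when < 1.4 mg/dL, within one week of the scheduled dose |
| > 5 mg/dL | Hold; no substitution and no make-up dose, stated as an explicit exception to the one-week late dose |

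The investigators should confirm the threshold. If they prefer the table's limits, the text should be changed to match, and they should state why pegaspargase may be given at values where Marqibo is withheld.

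The editing cost is one change to one section. The clinical cost is that some doses at 1.4 to 3 mg/dL, which the table would allow, would be delayed or missed.

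Optionally, 7.1 could ask for a chemistry draw shortly before each pegaspargase dose. That would cost sites some freedom in choosing draw days, and the correction above does not depend on it.

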7.2 Required Supportive Care Therapies During Protocol Treatment

The following supportive care measures are required by protocol:

- Antifungal prophylaxis (mandatory only for Cohorts A and B):
 - Non-azole based anti-fungal prophylaxis is **mandated** in all subjects enrolled in Cohorts A and B from the start of therapy until day 29, and ideally until neutrophil count recovery. All subjects are encouraged to continue antifungal prophylaxis beyond the treatment period especially if neutrophil count recovery has not occurred. Any exceptions must be discussed with the Study Chair or Vice Chair. (See protocol section 5.2).

- All azole therapy must be discontinued at least 1 week prior to the start of initiation of protocol therapy with Marqibo®.
- *Pneumocystis prophylaxis:*
 - PJP prophylaxis is **required**, with agents and dosing provided according to institutional guidelines. (See protocol section 5.2)
- Bowel prophylaxis
 - All patients must receive prophylaxis against constipation starting with the first dose of Marqibo unless there is diarrhea. (See protocol section 5.5 and Appendix 6)

7.3 Disease Evaluations During Therapy

All patients should have a bone marrow aspirate/biopsy and lumbar puncture and CBC to assess response on day 29 (+/- 2 days)**.

**For cohort C: Restaging studies should be performed on day 14 (+ 2 days) of cycle 1, with the exception of those patients who proceed to a second cycle. Cohort C, cycle 2 may start on Day 15 – 22 of cycle 1. If a second cycle is administered, a single restaging on day 14 (+2 days) of cycle 2 is required. In summary, a day 14 (+2 days) evaluation is required in all subjects at the completion of treatment on cohort C, either after cycle 1 (if a second cycle is not administered), or after cycle 2. A day 14 evaluation will not be required in either scenario in the presence of circulating peripheral blasts.

A bone marrow procedure need not be performed if the patient has an absolute peripheral blast count (APBC) greater than or equal to 2,500/ μ L in the peripheral blood.

If the marrow is hypoplastic, and counts have not recovered to ANC \geq 500/ μ L and platelets \geq 50,000/ μ L repeat CBC weekly until recovery or progression.

If the patient has a M1 marrow but has not achieved an ANC > 500/ μ L and platelets > 50,000/ μ L, repeat CBC weekly and bone marrow every 1-4 weeks until count recovery or relapse.

7.4 Research Studies

Participation in pharmacokinetic (PK) studies is mandatory for a limited sample set, for which samples can be drawn from the same line used to administer Marqibo®. Institutional guidelines should be followed in regard to maximum blood draw limits for pediatric patients.

Participation in the collection of the Dose 1 PK specimens is encouraged but is voluntary and patients may still participate in the therapeutic part of the study if they decline participation in

the research samples. Institutions are encouraged to talk to their patients about participation. The more detailed PK studies, require samples to be drawn from a line separate from the one used to administer Marqibo®.

7.4.1 Bone Marrow MRD

Samples requested:	
Bone Marrow Sample for MRD
 
 • Pre-treatment: optional* • Day 29 (+/- 2 days) 
Sample should also be submitted if the bone marrow procedure is repeated after day 29 to document marrow and count recovery. * Repeat bone marrow for this purpose is not required. For patients with circulating blasts, 10 mL of peripheral blood in a heparinized tube may be submitted. For all patients, prior flow cytometry report should be submitted.
 
*Bone Marrow MRDs are performed as part of standard of care, however, the information from them will be used for research purposes.
 
Not required for cohort C.

Bone marrow Collection procedure:	
 • Collect minimum of 2 mL of marrow into a syringe and place marrow into a large purple EDTA tube that are commonly used in all hospitals. Mix well. • Use multiple syringes and tubes as needed. Reposition marrow aspirate needle as least once during procedure to ensure the maximum quality of marrow
Specimen Labeling:	Please refer to the TACL MRD Lab Manual for instructions regarding specimen labeling.
Specimen Packaging and Shipping:	Please refer to the TACL MRD Lab Manual for instructions regarding specimen packaging and shipping.

*Results from MRD assessments must be forwarded to TACL Operations at [contact]

7.4.2 Marqibo® Pharmacokinetic Studies (Mandatory and Optional Studies)

Participation in PK studies is mandatory for a limited set, for which samples can be drawn from the same line used to administer Marqibo®. These studies include a baseline level drawn prior to the first dose and trough levels prior to the second and third dose of

Marqibo®. Participation in more detailed PK studies, which require samples to be drawn from a separate line than the one used to administer Marqibo® are voluntary. (Appendix 7).

The mandatory PK samples will be collected at the following time points for arm A and B.

- Generally performed 30-60 minutes before start of dose 1 infusion (SOI) ±10 minutes, but may be performed with routine morning labs as long as it is before start of infusion.
- Pre-dose #2 (trough level), up to 1 hour pre-dose is acceptable
- Pre-dose #3 (trough level), up to 1 hour pre-dose is acceptable

For cohort C, the mandatory PK samples will be drawn 30-60 minutes before start of dose 1 infusion (SOI) ±10 minutes, but may be performed with routine morning labs as long as it is before start of infusion; and a trough level will be drawn anytime on day 8.

The voluntary PK samples will be collected at the following time points (all cohorts):

- End of Infusion (EOI) of dose 1 ±5 minutes
- 3 hours (EOI + 2 hours) ±15 minutes
- 25 hours (EOI + 24 hours) ±30 minutes

Analysis will be conducted in the laboratory of the NCI POB Pharmacology and Experimental Therapeutics program. Quantification of total plasma vincristine will be performed by a qualified LC/MS/MS.

Samples requested:
	
Mandatory (Arm A & B)
 
 • Pre-dose 1 • Pre-dose #2 (trough level) • Pre-dose #3 (trough level) 
May be collected through the line used for Marqibo® infusion
 
Mandatory (Arm C)
 
 • Pre-dose 1 • Day 8 will have a trough level 	
Voluntary (all cohorts)
 
 • End of infusion (EOI) of dose 1 • 3 hours (EOI + 2 hours) • 25 hours (EOI + 24 hours) 
Must be collected from a separate line from that used for Marqibo® infusion.

----------------------------------	--	---

Sample Collection procedure:	
 Peripheral blood samples of 3 mL will be collected in lavender-top (EDTA) vacutainers at each of the time points indicated above. Invert the lavender-top vacutainer 10 times to mix completely If blood samples are taken via an indwelling central venous cannula, an appropriate amount of fluid should be removed from the cannula to clear the line before each blood sample is taken. Place the samples on ice until centrifugation
Specimen Processing	
 Plasma: should be separated by centrifugation at 10C (10 min at 1000 g or 2500 rpm) within four hours after collection. Separated plasma should be transferred to screw-capped polypropylene tubes (i.e. Nunc 3.6 ml #379189, 366524 or equivalent). Plasma samples should be stored in the dark at less than -70° C.
Specimen labeling:	
 Specimens should be labeled with the TACL registration number, date and time of sampling and the sample number (see appendix 7).

Specimen Packaging and Shipping:	
 • Participating sites should ship samples on dry ice using priority Federal Express. • Samples should be shipped Mon, Tues or Wed only and should not be sent on the day preceding a holiday. Lab receives samples Tuesday through mid-Friday. • All samples should be batched per patient • Send a notification email to [contact] when sending samples. • Include the completed pharmacokinetic worksheet (Appendix7) • Ship samples to: 
[name] Lab Clinical Pharmacology Program National Cancer Institute [name] [name][name] 20892 (O) [contact] (F) [contact]
 
For specimen shipping, please request a label from TACL Operations at least 24 hours in advance of shipment. Please call the TACL Operations Center for any questions at [contact].

---	--

